6.1 Sample Size Determination

6.2 This is a pilot study and therefore the anticipated number of patients included (20) represents an attainable number within the planned study period (1 year) based on the clinical volume of our group. Our group treats approximately 35-40 patients per year who would likely meet inclusion criteria for this trial. We estimate a cohort of 200 patients in a randomized trial will be required to demonstrate superiority of the technique, and a 10% sample of that cohort will be sufficient provide preliminary safety data as well as to demonstrate feasibility of a future trial.

6.3 Statistical Methods

The results of this study will be compared using a univariate analysis to historical control data obtained from the DHMC ACS-NSQIP database, with emphasis on surgical site occurrences including all types of SSI, and unplanned return to the operating room data points. The preliminary safety and feasibility data obtained from this study will be used to inform design of a larger study to test the hypothesis that the procedure can obtain a 50% reduction in the incidence of hernia formation at previous ileostomy sites compared to rates reported in the literature. The secondary objectives have not been previously reported in the literature either for patient reported outcomes or prospective evaluation of hernia formation. Further work, based on the data from this study, will attempt to show the superiority of the technique over currently used closure techniques as well as patient satisfaction with the procedure.

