12	PUBLICATION PLAN.....	12
13	REFERENCES.....	13
14	ATTACHMENTS.....	15

List of Abbreviations

CCRC – Clinical Cancer Review Committee
DSMAC – Data Safety Monitoring and Accrual Committee
mL - Milliliter
MRSA – Methicillin-resistant Staphylococcus aureus
NCCC – Norris Cotton Cancer Center
NCCN – National Comprehensive Cancer Network
SSI – Surgical Site Infection
S-SSI - Superficial surgical site infection
D-SSI – Deep surgical site infection
O-SSI – Organ space surgical site infection
SCIP – Surgical Care Improvement Project
PDS – Polydioxanone
SSO – Surgical Site Occurance

Study Summary

Title	Stoma Closure and Reinforcement Trial (SCAR) – Pilot Study
Short Title	SCAR Trial
Protocol Number	1
Phase	Pilot feasibility
Methodology	Open Label
Study Duration	The study is estimated to last 5 years
Study Center(s)	Single center – Dartmouth Hitchcock Medical Center
Objectives	
 1. To perform a pilot study to validate the mesh implantation procedure at the time of ileostomy closure. 2. To evaluate patient satisfaction and resource utilization associated with the procedure. 3. To prospectively evaluate the cohort for evidence of hernia formation at the previous stoma site. 4. Use data from this trial to design an appropriately powered, multi-center, prospective randomized, controlled trial of mesh reinforcement of ileostomy closures.
Number of Subjects	20
Diagnosis and Main Inclusion Criteria	
 1. Left sided colon or rectal cancer treated with resection and diverting loop ileostomy, with or without neoadjuvant or adjuvant therapy. 2. Age > 18years 3. Patient is undergoing elective closure of diverting loop ileostomy
Study Product, Dose, Route, Regimen	Bard™ Soft Mesh (Bard Davol, Inc): large pore, open weave, monofilament polypropylene mesh.
Duration of administration	The mesh would be implanted as a reinforcement of the stoma closure on a permanent basis. The mesh is not intended to be removed.
Reference therapy	Standard procedure for ileostomy closure
Statistical Methodology	No power calculation is necessary for this study since it is a pilot study. The results will be used to calculate power for future investigations.

1 Introduction

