1.4 Risk/Benefits

The primary concern is for surgical site occurrences. In the absence of mesh, the incidence of infection in ileostomy closures is estimated between 6 and 18%.⁴³⁻⁴⁵ This rate is minimized with the use of a purse string skin closure with iodine impregnated gauze packing vs partial closure with an open ended drain (Penrose type) or primary skin closure.⁴⁶ Prospective trial data estimates the overall incidence of infections when bioabsorbable mesh is placed in Class II and III ventral hernia repairs at 18%. None required mesh explantation and all wounds eventually healed.²⁷ Other reports of macroporous polypropylene mesh in clean-contaminated and contaminated wounds suggest an infection rate of 7.1% for clean contaminated and 19% for contaminated cases.²³ Surgical site occurrences will be treated on an individual patient basis determined by the clinical consequences of the occurrence. Infection may potentially be treated with antibiotics, local wound care, operative debridement, radiographically guided drainage procedures, vacuum assisted wound closure devices, or mesh removal at the discretion of the study team. Other potential adverse events are those inherent to intestinal surgery; anastomotic leak, peritoneal abscess formation, bowel obstruction, or ileus, in addition to the risks associated with general anesthesia.

2 Study Objectives

Primary Objective: To validate the technical procedure of mesh implantation at the time of ileostomy closure and preliminarily determine the incidence of surgical site occurrences (particularly those requiring intervention) compared to standard ileostomy closure technique.

Secondary Objective #1: Measure and compare quality of life scores for aspects related to the procedure to those related to bowel function.

Secondary Objective #2: To evaluate the process for longitudinally monitoring for the occurrence of hernia at site of stoma closure. We will evaluate our study protocol for the feasibility of performing a larger trial by measuring recruitment, retention of patients, adherence to the study protocol, and process assessment.

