By the completion of this pilot study, our expected outcomes are to have demonstrated a high level of procedural fidelity among the operating surgeons of the modified ostomy closure technique and comparable costs to the standard procedure as well as greater than 80% recruitment and retention of eligible participants, and greater than 90% adherence to the study protocol. We also expect to preliminarily demonstrate safety and similar quality of life compared to historical controls on short term follow-up. These results are expected to inform development of an appropriately powered, multiple center, randomized controlled trial comparing the effectiveness of our novel modification of ostomy closure technique to the standard technique.

3 Study Design

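### Twenty patients and an unspecified comparison with historical controls cannot support the preliminary safety conclusion the pilot expects; exact intervals should replace it

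*Combined protocol and SAP*

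**What the plan says.** Section 6.3 describes the analysis in one sentence: "The results of this study will be compared using a univariate analysis to historical control data obtained from the DHMC ACS-NSQIP database". The outcomes it stresses are surgical site occurrences, with infections of every type counted, and unplanned reoperation. Section 3.2 makes a comparison of 30-day wound occurrences with historical controls part of the primary endpoint.

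The expected result is in the closing paragraph of section 2: "We also expect to preliminarily demonstrate safety and similar quality of life compared to historical controls on short term follow-up".

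On sample size, the text numbered 6.2 estimates a future randomised trial of 200 patients and says that "a 10% sample of that cohort will be sufficient provide preliminary safety data as well as to demonstrate feasibility of a future trial". The Study Summary adds: "No power calculation is necessary for this study since it is a pilot study".

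The background rate for standard closure is in section 1.4: "In the absence of mesh, the incidence of infection in ileostomy closures is estimated between 6 and 18" percent. The local registry rate is not given.

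The document does not state a test, significance level, sidedness, confidence interval, acceptable margin, number or calendar period of controls, or any criterion by which preliminary safety would be judged.

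**The concern.** The expected conclusion is comparability with historical controls. The only analysis offered is a comparison whose form and size are left open, and nothing connects the two. If the comparison is carried out as an ordinary significance test, the likely result with 20 patients is no significant difference, whether or not the mesh doubles wound infection. The result would then reflect the size of the study more than the safety of the procedure.

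This matters because sections 2 and 6.3 say that the pilot's safety data will inform a multicentre randomised trial of a permanent implant placed during bowel surgery. Readers of the pilot need to know how large an excess of wound events 20 patients leave open. The plan as written would not tell them.

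**Working it through.** **Inputs from the document.** Mesh patients: n = 20 (section 6.2). No-mesh infection rate: 6% to 18% (section 1.4). Retention expected above 80% (section 2), with patients lacking complete follow-up excluded from the final analysis (section 6.4).

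**Assumptions, none of them stated in the plan.** Two-sided 5% test; 20 to 500 controls; a doubling of the infection rate as the harm to be detected.

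**The plan's own figure.** 10% × 200 = 20. The arithmetic reproduces, but it is a proportion of another trial's size and says nothing about precision or detectable harm.

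**Step 1: probability of missing a doubling.** Let X ~ Binomial(20, 2p) be infections with mesh and Y ~ Binomial(m, p) infections among m controls. The miss probability is 1 − Σ P(X = x)·P(Y = y), summed over all (x, y) where the mesh rate is higher and the test gives P ≤ 0.05.

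| Controls m | Fisher, 6%→12% | Fisher, 18%→36% | Pearson, 6%→12% | Pearson, 18%→36% |
|---|---|---|---|---|
| 20 | 97% | 84% | 93% | 75% |
| 40 | 89% | 73% | 87% | 66% |
| 100 | 86% | 62% | 81% | 55% |
| 200 | 84% | 58% | 76% | 51% |
| 500 | 82% | 55% | 76% | 49% |

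For 12%→24%, Fisher's test misses 74% with 100 controls and 70% with 200. If the historical rate is treated as fixed and an exact binomial test is used, rejection needs at least 4 of 20 when p = 6% (miss 79%) and at least 8 of 20 when p = 18% (miss 56%). The overall range is about 50% to 97%. Fisher's test with 100 to 200 controls gives 58% to 86%.

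In counts, with Fisher's test against 100 controls: 6/20 (30%) against 12/100 gives P = 0.078, and 7/20 (35%) against 18/100 gives P = 0.13. Both are non-significant, although the observed rates are 2.5 times and about twice the control rate.

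**Step 2: precision of the rate itself.** Exact (Clopper-Pearson) 95% intervals for n = 20:

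| Events | Rate | 95% interval |
|---|---|---|
| 0 | 0% | 0–16.8% |
| 1 | 5% | 0.1–24.9% |
| 2 | 10% | 1.2–31.7% |
| 3 | 15% | 3.2–37.9% |
| 4 | 20% | 5.7–43.7% |

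For zero events the upper limit is 1 − 0.025^(1/20) = 16.8%; the one-sided 95% limit is 1 − 0.05^(1/20) = 13.9%. If the control rate is 6%, even 0/20 does not exclude a doubling to 12%. If it is 18%, a doubling to 36% is excluded only with 2 or fewer events.

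**Step 3: fewer evaluable patients.** At 80% retention, 0.8 × 20 = 16. The upper limit for 0/16 is 1 − 0.025^(1/16) = 20.6%. Fisher's test with 100 to 200 controls then misses a doubling in 63% to 87% of trials.

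**The case against.** The authors present this as an unpowered pilot. They qualify the safety aim with the word preliminarily in section 2, and write of preliminary safety data in sections 6.2 and 6.3. That stands: the plan does not claim a definitive demonstration of safety. The qualifier lowers the strength of the claim, but it supplies no criterion for reaching it.

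A reader might infer that the plan intends to treat a non-significant test as proof of safety. The document does not support that. It names no test and no decision rule, and a univariate comparison could be no more than rates set side by side. What can be said is that the plan neither defines the comparison nor rules that reading out.

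A reader might also take 58-86% as a property of this trial. It is not. It needs Fisher's test, a two-sided 5% level, 100 to 200 controls and a doubling as the target. Since the group sees only 35 to 40 likely eligible patients a year (section 6.2), fewer controls are possible, and the miss probability would then be higher.

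It is tempting to set the 3/20 interval against the 31% surgical site occurrence rate in section 1.3.1 as well. That figure covers a wider outcome in a different operation, ventral hernia repair with mesh, so it is not a benchmark for the infection calculation here.

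Finally, safety during the study does not rest on this comparison. There is a five-patient first stage (section 3.1), there are suspension rules (section 7.4), and the monitoring committee reviews the study quarterly (section 9.1). These protections are real. However, the first-stage rule and the suspension rules act on return to the operating room, mesh removal, death or severe morbidity, and none of the three sets a criterion for the overall infection and surgical site occurrence rates that sections 3.2 and 6.3 compare.

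**Conclusion.** The point holds as a gap between the expected conclusion and the stated analysis. The plan gives no interval, control number or criterion for its preliminary safety conclusion, and it does not support its statement that "a 10% sample of that cohort will be sufficient provide preliminary safety data" with any figure for precision. If the comparison is a two-sided 5% test, a doubling of the 6-18% infection rate would be missed in about 50-97% of trials. That range rests on the assumed tests, 20 to 500 controls and the choice of a doubling; at 20 patients every version shown misses it about half the time or more. The exact intervals in Step 2 rest only on n = 20. The calculation concerns infection; no background rate is given for surgical site occurrence or return to the operating room in standard closure, so the same sum cannot be done for those. The point does not show that the procedure is unsafe, or that the investigators will misread the result.

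**What to change.** - **Section 6.3.** Report each 30-day rate (surgical site occurrence, surgical site infection, return to the operating room) with its exact 95% confidence interval, and the difference from the registry rate with a 95% confidence interval by a named method. State the number and calendar period of the controls. Report the largest excess the interval does not exclude. State that a non-significant difference will not be taken as evidence of safety.
- **Section 6.2.** Replace the word sufficient with the precision that 20 patients give: 0/20 has an upper 95% limit of 16.8%, and 3/20 has an interval of 3.2% to 37.9%.
- **Section 2.** Change the expected outcome from preliminarily demonstrating safety to preliminarily estimating the 30-day surgical site occurrence rate. This agrees with the primary objective, which already speaks of determining an incidence.

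The cost is wording in three sections and a less favourable stated claim. No extra patients are needed.

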6.4 Subject Population(s) for Analysis

The statistical analysis for this study will use an all-treated population: Any subject who participated in the study and underwent the study procedure. Patients without complete follow-up data will be excluded from the final analysis.

7 Safety and Adverse Device Effects

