3.2 Primary Study Endpoints

The primary end point of the study is the validation of the mesh implantation procedure. We will assess the incidence of wound occurrences (defined as S-SSI, D-SSI, organ space SSI, dehiscence, and seroma formation) at 30days, with particular attention to wound occurrences requiring procedural intervention, including but not limited to, operative debridement, radiographically guided drain placement, or excision of the mesh. These incidences will be compared to historical controls.

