4.4 Early Withdrawal of Subjects

4.4.1 When and How to Withdraw Subjects

Patients may be withdrawn from the study at any time based upon withdraw of consent. Patients may also be withdrawn if the study treatment cannot be tolerated (i.e. removal of mesh device is required). Patients must continue to participate for 30days post-operatively in order for inclusion in the analysis of the primary endpoint data.

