4.4.2 Data Collection and Follow-up for Withdrawn Subjects

Data related to the time period of the subject's participation will be included in the analysis of the treatment effect. Should a subject be withdrawn from the study for any reason, survival data will be maintained in accordance with the guidelines for follow-up prescribed by the NCCN.

5 Study Procedures

5.1 Encounter 1

Patients will be assessed for ileostomy closure based upon completion of therapy after primary resection of their malignancy. Appropriate candidates will be determined at the operating surgeon's discretion based on customary evaluation of clinical status. The informed consent process will be initiated and the patient recruited into the study.

5.2 Encounter 2

This encounter is the operative procedure. The procedure for closing the ileostomy (i.e. bowel anastomosis) will be at the discretion of the surgeon, provided it is performed through the ileostomy site without additional laparotomy incisions. In accordance with SCIP guidelines, pre-operative intravenous antibiotic and subcutaneous pharmacologic venous thromboembolism prophylaxis will be administered. Patients with a history of MRSA infection will also receive a dose of intravenous vancomycin prior to the procedure.

The abdominal wall reconstruction portion of the procedure will be standardized to ensure consistency between surgeons. The posterior rectus sheath is closed with native tissue either primarily, using hernia sac if present, or bridged with Vicryl-type mesh and a quickly absorbing suture material. This is done to isolate the mesh from the peritoneal cavity. The retrorectus plane is developed using electrocautery and blunt dissection to provide adequate placement of mesh such that it overlaps the posterior sheath defect by a minimum of 3cm on all sides. The mesh is placed in this plane and secured in place with slowly absorbable monofilament (0-PDS preferred) sutures placed through the anterior fascia or with application of fibrin sealant at the surgeon's discretion. This space is then irrigated with

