7.1 Definitions

Unanticipated Problems Involving Risk to Subjects or Others

Any incident, experience, or outcome that meets all of the following criteria:

- Unexpected in nature, severity, or frequency (i.e. not described in study-related documents such as the IRB-approved protocol or consent form, the investigators brochure, etc)
- Related or possibly related to participation in the research (i.e. possibly related means there is a reasonable possibility that the incident experience, or outcome may have been caused by the procedures involved in the research)
- Suggests that the research places subjects or others at greater risk of harm (including physical, psychological, economic, or social harm).

Adverse Event

An **adverse event** (AE) is any symptom, sign, illness or experience that develops or worsens in severity during the course of the study. Intercurrent illnesses or injuries should be regarded as adverse events. Abnormal results of diagnostic procedures are considered to be adverse events if the abnormality:

- results in study withdrawal
- is associated with a serious adverse event
- is associated with clinical signs or symptoms
- leads to additional treatment or to further diagnostic tests

- is considered by the investigator to be of clinical significance

Unanticipated Adverse Device Effect (UADE):

An unanticipated adverse device effect is any serious adverse effect on health or safety, or any life-threatening problem or death, caused by or associated with an investigational device. Internal Unanticipated Adverse Device Effects (UADE) reports must be made within 10 working days.

Adverse Event Reporting Period

The study period during which adverse events must be reported is normally defined as the period from the initiation of any study procedures to the end of the study treatment follow-up. For this study, the study treatment follow-up is defined as 90 days following hospital discharge from the ileostomy closure procedure

Preexisting Condition

A preexisting condition is one that is present at the start of the study. A preexisting condition should be recorded as an adverse event if the frequency, intensity, or the character of the condition worsens during the study period.

General Physical Examination Findings

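### Section 6.4 names an all-treated population and then excludes patients with incomplete follow-up; this conflicts with section 4.4.2 and can remove observed primary-endpoint events from the reported rate

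*Combined protocol and SAP*

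**What the plan says.** Four statements in the combined protocol and SAP bear on who is analysed.

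- Section 6.4, first sentence: "The statistical analysis for this study will use an all-treated population: Any subject who participated in the study and underwent the study procedure".
- Section 6.4, second sentence: "Patients without complete follow-up data will be excluded from the final analysis".
- Section 4.4.1, on the primary endpoint: "Patients must continue to participate for 30days post-operatively in order for inclusion in the analysis of the primary endpoint data".
- Section 4.4.2, on withdrawn subjects: data from their period of "participation will be included in the analysis of the treatment effect".

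Two more statements show how these rules meet the endpoint. Section 4.4.1 gives mesh removal as a ground for withdrawal: "Patients may also be withdrawn if the study treatment cannot be tolerated (i.e. removal of mesh device is required"). Section 3.2 counts wound occurrences at 30 days, with particular attention to those needing a procedure, and its examples are "operative debridement, radiographically guided drain placement, or excision of the mesh". It continues: "These incidences will be compared to historical controls".

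The plan does not say what makes follow-up complete. It mentions several periods: 30 days (section 4.4.1), 90 days after discharge (section 7.1), 6 months (section 1.1), two years (section 3.3) and 5 years after cancer treatment (section 5.3).

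**The concern.** For a treated patient who leaves early, the two sentences of section 6.4 give opposite instructions, section 4.4.2 sides with the first, and nothing says which prevails. Two analysts could take the same 20 patients and report different event counts and denominators.

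The exclusion is also not neutral. Under section 4.4.1 a wound complication that leads to mesh removal can itself end participation, so the chance of being excluded depends on the outcome being measured. The resulting rate goes into the comparison with historical controls (sections 3.2 and 6.3) and into the design of the later randomised trial (section 6.3). For hernia, applying the exclusion sentence would discard hernias already seen in patients who later leave.

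**Working it through.** **The plan's own figure.** Section 6.1/6.2 sets N = 20 as 10% of an estimated 200-patient trial: 0.10 × 200 = 20. The stages in section 3.1 agree: 5 + 15 = 20. All counts below use n = 20. The event and dropout counts are illustrations, not predictions.

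**The rules applied to one patient.** Suppose the mesh is excised for a wound occurrence before day 30 and the patient is withdrawn.

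| Rule | Is the event in the primary rate? |
|---|---|
| 6.4, first sentence | Yes |
| 6.4, second sentence | No |
| 4.4.1, 30-day requirement | No |
| 4.4.2 | Yes |

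Reading *complete* as 30 days does not help, because this patient fails that test too.

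**Effect of that single patient** (exact Clopper-Pearson 95% intervals):

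- Kept: 1/20 = 5.0% (0.1% to 24.9%).
- Excluded: 0/19 = 0% (0% to 17.6%).

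**General form.** Let x events be observed among n treated patients, and let m patients be excluded, k of them with an event already observed.

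- Rate under the exclusion: (x − k)/(n − m).
- Range the observed data allow: from x/n (no excluded event-free patient has an event) to (x + m − k)/n (all of them do).
- The rate under the exclusion is below the lower limit when (x − k)/(n − m) < x/n, which simplifies to k/m > x/n. That is, excluded patients had observed events more often than the treated group as a whole.
- It cannot exceed the upper limit, because that limit adds m to both numerator and denominator of the same fraction.

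**30-day illustration.** x = 3, n = 20, m = 2 (one withdrawn for mesh excision before day 30, one event-free and lost before day 30), k = 1.

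- Under the exclusion: (3 − 1)/(20 − 2) = 2/18 = 11.1%.
- Allowed by the data: 3/20 = 15.0% to (3 + 1)/20 = 20.0%.
- Check: k/m = 50% exceeds x/n = 15%, so the reported rate is below anything the data permit. The exact interval for 3/20 is 3.2% to 37.9%.

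**Hernia illustration.** x = 7, n = 20, m = 4, k varied.

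| k | Under the exclusion, (7 − k)/16 | Allowed by the data, 7/20 to (11 − k)/20 |
|---|---|---|
| 0 | 43.8% | 35% to 55% |
| 1 | 37.5% | 35% to 50% |
| 2 | 31.3% | 35% to 45% |
| 3 | 25.0% | 35% to 40% |
| 4 | 18.8% | 35% |

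The rate can move either way from the observed 35%. From k = 2 (2/4 = 50% > 35%) it falls below the possible range. All five values lie inside the exact interval for 7/20, 15.4% to 59.2%.

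**Frequency.** This cannot be derived from the documents. Section 1.3.1 cites 4% mesh removal, but from a different cohort and with no stated period, and withdrawal under section 4.4.1 is discretionary.

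**The case against.** The strongest reply is that section 4.4.1 is specific to the primary endpoint and should be applied ahead of the general sentence in section 6.4. A patient with a wound event on day 20 who misses a later hernia visit would then stay in the primary analysis, and the exposure shrinks to withdrawals before day 30. This is a reasonable reading, but the plan does not state it, and it leaves the mesh-excision case open. It does show that section 4.4.1 causes part of the problem, so deleting the sentence in section 6.4 is not enough.

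Two of the listed periods are weak candidates for completeness. The 90 days belongs to adverse event reporting ("the study treatment follow-up is defined as 90 days following hospital discharge from the ileostomy closure procedure"), and the 5 years describes visits tied to cancer surveillance. That is fair. For hernia the real ambiguity is mainly 6 months against two years, and it remains.

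An early mesh excision would not go unnoticed. Adverse events are recorded (section 7.2), mesh removal at a return to the operating room for a wound occurrence suspends the trial and is notified (section 7.4), the stage-1 rule is separate (section 3.1), retention is measured (section 2) and missing data must be explained (section 8.3). All of this stands and limits concealment. None of it puts the event back into the analysed rate. Likewise, section 4.4.2 would keep hernias seen before withdrawal, so the fault for hernia is an unresolved conflict and not a settled discard.

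The illustrations were chosen, and 7/20 is close to the one-third rate that section 1.1 gives without reinforcement. With 3 hernias, 4 leavers and 1 of those already herniated, the result is 2/16 = 12.5% against 3/20 = 15.0%, a shift of 2.5 points. The shift is indeed small, but 12.5% is still below the lower limit, since 1/4 = 25% exceeds 15%. Shifts of this kind are smaller than the sampling error in a 20-patient pilot. An interval discloses sampling error, however; it does not disclose an omitted event.

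**Conclusion.** The concern holds and should be fixed. The contradiction is in the text itself: sections 4.4.1, 4.4.2 and 6.4 give incompatible analysis rules, and following the exclusion can drop an observed primary-endpoint event under any reading of complete follow-up. The size is one event in 20 (5.0% becoming 0%) in the simplest case, or 11.1% where the data allow 15.0% to 20.0% in the illustration. This depends on a discretionary withdrawal before day 30 and on the exclusion prevailing over section 4.4.2. Confidence in the contradiction is high; its frequency is unknown and its direction is not fixed. The consequence is confined to the reported rates and to what they feed in the later trial, and does not touch participant protection.

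**What to change.** Delete the exclusion sentence in section 6.4 and have sections 4.4.1, 4.4.2 and 6.4 state one analysis rule: everyone who undergoes the study procedure is analysed, and every wound occurrence or hernia observed before withdrawal, loss or death counts. The 30-day participation requirement in section 4.4.1 should no longer decide who enters the primary analysis. The clinical grounds for withdrawal need not change.

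- **30-day endpoint.** Report observed events over all treated patients with an exact 95% interval. State how many event-free patients were lost before day 30, and give bounds counting them first as all event-free and then as all having events. The bounds are needed because the headline rate alone treats those losses as event-free.
- **Hernia.** Define what counts as complete follow-up at each scheduled visit. Report observed hernias with stated denominators and the same bounds. A cumulative incidence estimate is optional.

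This changes wording only and needs no extra patients, visits or data. It costs an amendment submitted to the IRB and slightly more analysis work, and the reported rates may be less favourable.
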